8.5.1.1 XR-NTX Injections

Following a negative naloxone challenge (see MOP), XR-NTX monthly injections begin. XR-NTX (4cc, ~380mg of naltrexone base) is administered approximately every four weeks (with the final injection occurring no later than week 22), in the form of Vivitrol[®] which is obtained by NIDA or the NIDA contractor for distribution to the sites. XR-NTX injections may take place <4 weeks apart if there is clinical concern about non-adherence (participant is inconsistent in attending scheduled visits) or if clinical observation is that opioid craving and/or use re-emerge during the 4th week after the last injection; however, time between injections must always be at least 21 days. XR-NTX is administered by intramuscular injection to the buttocks (alternating sides) according to the injection preparation and administration procedures specified in the Vivitrol[®] product package insert (see Appendix C). These procedures are designed to minimize the risk of injection site reactions.

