8.5.1.3 Handling of Missed XR-NTX Doses, Lapses, and Relapses

Use of illicit opioids presents different concerns in the management of patients receiving XR-NTX maintenance, compared to those receiving BUP-NX. Because of the long duration of action of XR-NTX (full blockade out to 5 weeks after the last injection¹⁷), a grace period of 7-21 days can be expected during which the injection can be rescheduled, provided the participant has not relapsed and become re-dependent. If the participant misses a scheduled injection and does not otherwise meet the primary outcome of relapse, XR-NTX may then be continued following a negative naloxone challenge (if clinically indicated) up to 21 days after a missed dose (49 days post prior injection; see MOP).

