8.5.3 Dispensing of XR-NTX and BUP-NX

Study medications (XR-NTX and BUP-NX) are provided by the study at no cost to the participant. XR-NTX is administered in-clinic at induction and approximately every four weeks with the final injection occurring no later than week 22. BUP-NX is dispensed to participants at induction and at treatment weeks 1, 2, 3, 4, 6, 8, 10, 12, 14, 16, and 20. Medication may be dispensed more frequently at the discretion of the study clinician. In addition, for participants receiving BUP-NX who are discontinued, who do not wish to continue, or for whom community resources to continue are not available, the study may dispense sufficient BUP-NX for up to a two-week taper beginning at any time during treatment or beginning at the week 24 visit. BUP-NX dose adjustments or emergency medication replacement between visits are allowed and will necessitate as-needed treatment and medication-dispensing visits. The clinical team may extend the window for medication administration or dispensing by up to three weeks if (a) the participant is abstinent (both self-report and urine are negative), (b) can restart the originally assigned medication, and (c) the treatment lapse is scheduled (i.e., the participant has provided a credible reason for the lapse and remains in contact with the study team).

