Phase 1: Informed Consent, Screening, and Randomization (Days -15 through Day 0): This phase begins with informed consent during the index admission, and initiates enrollment, the conduct of all study-specific procedures and the collection of study data. During the first several days of an index admission, clinical and/or research staff will provide information about the study to potential participants (for scheduled admissions this information may be provided in advance of the admission). Guidelines for opioid detoxification are provided in the study MOP; data on detoxification utilization will be collected. This phase may take place from 1 day to 15 days. Following final review and confirmation of all eligibility criteria, randomization may proceed. Randomization may take place on the same day as informed consent and screening if recent liver function results are available, but in most cases will likely take place 2 or 3 days

later. Regardless of when randomization takes place, the date of randomization will be defined as “Day 0”.

Phase 2: Induction (Day 0 through Day 156): Following randomization, participants will be inducted onto their assigned active medication condition and treated as outpatients for 24 weeks per protocol. Guidelines for induction onto XR-NTX and onto BUP-NX are provided in the study MOP. Following induction, XR-NTX will be administered by injection approximately every 4 weeks; and BUP-NX will be quickly titrated upwards to maintenance doses. Induction should occur as soon as practicable following randomization, but may occur as late as week 22. Participants will continue into Phases 3 and 4 for research visits, even if not yet inducted onto their assigned medication.

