¹ Number of Visits ‘Present and Clean’ is based on the UDS results evaluated starting at Day 21 and up until the point of relapse. A UDS result which is within temperature range and deemed to be unadulterated and is not positive for non-protocol prescribed opioids is categorized as present and clean. A complete number of UDS results ‘Present and Clean’ is defined for each participant.

[figure not shown]
Table 22: Summary of Number Completing 24 Weeks of Treatment¹ for the Groups of Interest				
	BUP-NX (N=)		XR-NTX (N=)	
	Completed 24 Weeks of Treatment N (%)	Didn't Complete 24 Weeks of Treatment N (%)	Completed 24 Weeks of Treatment N (%)	Didn't Complete 24 Weeks of Treatment N (%)
Total				
Randomization Timing Status				
Early Randomizers				
Late Randomizers				
Opioid Severity Level ¹				
Low Severity				
High Severity				
Randomization Timing Status by Opioid Severity Level				
Early Randomizers and Low Severity				
Early Randomizers and High Severity				
Late Randomizers and Low Severity				
Late Randomizers and High Severity				
Baseline Preference ²				
Preferred Neither Treatment				
BUP-NX Preference				
XR-NTX Preference				
Preferred Either Treatment				
Inducted onto Study Medication				

¹ A participant is defined as completing 24 weeks of treatment if he/she received XR-NTX in Week 20-24 or was dispensed BUP-NX during Week 20-24.

Table 23: Summary of Trails A and B by Treatment Arm

	Treatment Arm																	
	BUP-NX (N=)						XR-NTX (N=)						Total (N=)					
	Week 0	Week 4	Week 8	Week 16	Week 24	EOT	Week 0	Week 4	Week 8	Week 16	Week 24	EOT	Week 0	Week 4	Week 8	Week 16	Week 24	EOT
Trails A																		
N																		
Mean																		
SD																		
Median																		
Min																		
Max																		
Trails B																		
N																		
Mean																		
SD																		
Median																		
Min																		
Max																		

Figure 10: Boxplots of Trails A by Treatment Arm

Example figure provided.

Figure 11: Boxplots of Trails B by Treatment Arm

See example figure provided above for details.

Table 24: Summary of Stroop Color and Word Scores by Treatment Arm																		
	Treatment Arm																	
	BUP-NX (N=)						XR-NTX (N=)						Total (N=)					
	Week 0	Week 4	Week 8	Week 16	Week 24	EOT	Week 0	Week 4	Week 8	Week 16	Week 24	EOT	Week 0	Week 4	Week 8	Week 16	Week 24	EOT
Word Score																		
N																		
Mean																		

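### SAP Table 22 treats one injection or dispensing in weeks 20-24 as completing 24 weeks of treatment, so late starters and some BUP-NX stoppers count as completers, while an adherent XR-NTX patient started in week 3 may not

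*SAP*

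**What the plan says.** - **Completion rule.** SAP Appendix A, Table 22 tabulates completion of 24 weeks of treatment by arm, randomization timing, opioid severity, baseline preference and induction. Its footnote 1 asks only that the participant "received XR-NTX in Week 20-24 or was dispensed BUP-NX during Week 20-24".
- **Latest start.** SAP Section 1.2: "Induction should occur as soon as practicable following randomization, but may occur as late as week 22". Protocol Table 3 gives days 0-156 for induction in both arms.
- **XR-NTX schedule.** Protocol Section 8.5.3: "XR-NTX is administered in-clinic at induction and approximately every four weeks with the final injection occurring no later than week 22". Section 8.5.1.1 adds "XR-NTX injections may take place <4 weeks apart if there is clinical concern about non-adherence", or if craving or use returns in the fourth week, but "time between injections must always be at least 21 days". Section 8.5.1.3 lets a missed injection be made up until 49 days after the previous one.
- **BUP-NX schedule.** Protocol Section 8.5.3 makes week 20 the last scheduled maintenance dispensing. It also allows a taper of up to two weeks, including for participants who are discontinued, "beginning at any time during treatment or beginning at the week 24 visit". Section 8.5, part A, allows only taper to be dispensed at week 24. A footnote to Protocol Table 3 allows taper on discontinuation in weeks 1-22.
- **Ending early.** Protocol Section 10.1 treats ending before week 21 as ending treatment early.

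**The concern.** The table title describes a duration. The footnote tests for one contact with medication near the end of the period. Because first induction may be very late and taper may be given to someone who is stopping, that contact does not show that 24 weeks of treatment took place. For XR-NTX, the last-injection limit also leaves only weeks 20-22 of the stated window usable, and a regular four-week schedule can step over it.

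At stake is how retention is reported by arm. Protocol Appendix B, Section 1.0, names retention among the secondary comparisons. Table 22 is split by randomization timing, and Protocol Section 12.3 expects XR-NTX induction to be harder for early randomizers. Any error may therefore differ between the cells being compared.

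**Working it through.** The plan gives no count or rate for this rule, so there is no figure to reproduce. I first checked the calendar and then applied the footnote.

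**Calendar.** SAP Table 3 sets the target day of week k at 7k - 1, with a window of 3 days either side from week 2 on.
- Week 3: target 20, days 17-23.
- Week 19: target 132, days 129-135.
- Week 20: target 139, days 136-142.
- Week 22: target 153, days 150-156. This agrees with the stated last induction day of 156.
- Week 24: target day 167.
- Make-up limit: 28 + 21 = 49 days, as the protocol states.

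**Late first doses.** A first dose in weeks 20-22 falls on days 136-156. Time left to the week-24 target is 167 - 136 = 31 days at most and 167 - 156 = 11 days at least. One such dose, in either arm, meets the footnote.

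**BUP-NX stoppers.** The footnote asks for any dispensing in weeks 20-24 and does not exclude taper.
- A taper begun in weeks 20-23 on discontinuation passes.
- A taper begun at week 24 with no week-20 maintenance dispensing passes.
- Maintenance dispensed at week 20 followed by stopping within days also passes, although the participant may have ended early under Protocol Section 10.1.

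**XR-NTX started in week 3, exact 28-day spacing.**

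| Injection | Days | Week |
|---|---|---|
| 1 | 17-23 | 3 |
| 2 | 45-51 | 7 |
| 3 | 73-79 | 11 |
| 4 | 101-107 | 15 |
| 5 | 129-135 | 19 |
| next due | 157-163 | 23 |

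The sixth injection would fall after day 156 and is not allowed. This participant had all five injections due, none in weeks 20-22, and fails the footnote.

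**Is that failure forced?** No, for three reasons.
1. If intervals may vary over 25-31, 21-28, 21-35 or 21-49 days, there is no start week from which passing is impossible. As an illustration only, intervals assumed uniform on 25-31 days give 54% failing from a week-3 start. Uniform on 21-35 days gives 29%. The documents give no interval distribution.
2. Injections are given at Medical Management visits (Protocol Section 8.5, part A), scheduled in weeks 0-4, 6, 8, 10, 12, 14, 16, 20 and 24. From week 3, with gaps of 3-7 weeks (21-49 days), there are seven sequences confined to these visits, such as 3-8-12-16-20. All seven end in week 20 and pass.
3. SAP Table 12 has a row for seven injections. At 28-day spacing from day 0 only six fit (days 0, 28, 56, 84, 112, 140). Seven by day 156 need a mean interval of at most 156/6 = 26 days, so the SAP itself provides for intervals under 28 days.

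**The case against.** The best defence is that this is a descriptive shell with no test. Completion of 24 weeks is neither the primary outcome nor listed in SAP Table 1. A check from week 20 onward is broadly in line with the protocol's own meaning of ending early. Time to induction, early medication terminations, exposure and injection counts appear in SAP Tables 6, 8, 11 and 12. All of this stands and limits the importance of the point. It does not make the footnote measure what the title says.

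A reader might infer more than the documents support:
- **That XR-NTX starts in weeks 3, 7, 11, 15 and 19 fail by design.** The list is correct at exact 28-day spacing, but spacing is only approximate. Starts in weeks 7, 11, 15 and 19 give 4, 3, 2 and 1 injections on that schedule. None is 24 weeks of treatment, so failing them is right. Only the week-3 start is a plausible false non-completer among the five.
- **That a quarter of XR-NTX participants are affected.** Such a figure counts calendar weeks, not people. Protocol Table 1 marks the first injection at weeks 1 and 2. At exact spacing these end in weeks 21 and 22 and pass.
- **That the rule favours BUP-NX.** Late one-dose XR-NTX inductees inflate the XR-NTX figure, and late first BUP-NX dispensing does the same in the other arm. No net direction follows.
- **That every week-24 taper is a false completion.** It usually follows week-20 maintenance dispensing and treatment to week 24. The problem cases are those set out above.

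**Conclusion.** The point holds in limited form. By the wording alone, Table 22 counts as completers of 24 weeks:
- participants in either arm whose first dose was in weeks 20-22;
- BUP-NX participants whose only qualifying dispensing was a taper begun in weeks 20-23, or at week 24 with no week-20 maintenance dispensing.

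These need no assumption beyond the stated schedule. The opposite error, an adherent week-3 XR-NTX start classed as a non-completer, rests on spacing at or close to 28 days and is possible but not forced.

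Misclassification can therefore go both ways. Its size depends on induction delays that the documents do not give, and its net effect on the arm comparison is unknown. It is a minor reporting defect in a descriptive retention table. The primary outcome is untouched.

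**What to change.** Change the Table 22 footnote and derivation before the table is run:

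1. Count only non-taper BUP-NX dispensing, and require that medication was not discontinued before the end of the treatment period. State the cut-off once and reconcile it with the meaning of ending early, before week 21, in Protocol Section 10.1.
2. In both arms, show participants with late first induction in a separate row, not among completers of 24 weeks. The documents give no cut-off for late, so one must be fixed in advance. Alternatively, retitle the table *On study medication in weeks 20-24*. Retitling deals with late inductees only, so items 1 and 3 are still needed.
3. For XR-NTX, do not class as a non-completer a participant inducted in the first weeks who received every injection due before the week-22 limit. A cut-off at day 23, the end of the week-3 window, would cover the worked case.

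Do not build this on the expected-dose counts in SAP Table 11. They start at induction, so a single first dose in week 21 would be one of one due. They also stop at relapse, so an early relapser with every injection to date would appear complete.

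The cost is a footnote, a derivation and one added row per arm, with no new data. Injection, dispensing and end-of-medication dates are already collected. I assume that taper can be told apart from maintenance in the dispensing records. Protocol Table 3 lists it separately, but if the dose log does not flag it, the end-of-medication date can be used.

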5.2 Secondary Objectives

Secondary objectives are to:

1. Compare outcome on XR-NTX versus BUP-NX for the following domains:
 - a. Proportion successfully inducted onto assigned medication.
 - b. Safety, as measured by adverse events and serious adverse events, including opioid overdose episodes, both during the 6-month trial and during the 3-month follow-up period.
 - c. Opioid abstinence, as measured by the Timeline Follow-Back (TLFB) (self-report days using opioids), proportion of opioid-positive urine tests.
 - d. Misuse of alcohol and other drugs of abuse (e.g., cocaine, other stimulants, cannabis, benzodiazepines), by self-report and urine drug screens.
 - e. Tobacco use, as measured by the Fagerström Test for Nicotine Dependence (FTND).
 - f. Craving for opioids, and for other drugs, measured by Visual Analog Scales (VAS).
 - g. Depressive, anxiety, and subacute withdrawal symptoms (typical constellation is fatigue, anorexia, and insomnia), as measured by the Hamilton Depression Scale (17-item) (HAM-D) and the Subjective Opioid Withdrawal Scale (SOWS).
 - h. Problems related to drug abuse, as measured by the Addiction Severity-Index-Lite (ASI-Lite) and EuroQol (EQ-5D).
 - i. HIV risk behavior over time, as measured by the Risk Assessment Battery (RAB).
 - j. Cognitive function, as measured by performance on brief pen and paper tasks (Trail Making Test Parts A and B, Stroop).
2. Explore baseline demographic, clinical, and genetic features as predictors of opioid use outcome over the 6-month trial (main effect of predictors), and as moderators of differential treatment effect (moderator by treatment interaction).
3. Collect a limited dataset to permit analyses of economic costs and benefits of the two treatments.

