9.2 Secondary Outcomes

Table 2: Protocol Secondary Outcomes and Hypotheses

Outcomes	Hypotheses
Proportion successfully inducted onto assigned study medication (binary: did or did not receive first dose of XR-NTX, or achieve maintenance dose of BUP-NX)	BUP-NX will produce higher rate of successful induction than XR-NTX Significance/Rationale: XR-NTX induction requires completion of detoxification, whereas BUP-NX induction only requires onset of withdrawal symptoms. Thus XR-NTX may have more dropouts after randomization but prior to XR-NTX induction.
Adverse Events related to study medications	XR-NTX and BUP-NX will produce equivalent rates of SAEs, and equivalent rates of AEs, though AE pattern will differ somewhat (e.g. injection site reactions with XR-NTX) Significance/Rationale: Careful documentation of SAEs and AEs, including overdose episodes, would be considered essential safety data, and important component of a comparative effectiveness trial.
Opioid abstinence over time while on study medication (Weekly TLFB, confirmed by urine drug screens)	XR-NTX will produce greater opioid abstinence than BUP-NX Significance/Rationale: XR-NTX produces complete blockade of opioid effects, so that during treatment with monthly injections, opioid use can be expected to be minimal. In contrast BUP-NX may not produce complete blockade, or patients may reduce or stop doses for a few days and substitute other opioids (heroin, prescription opioids).

Outcomes	Hypotheses
Alcohol and other drug use, over time (TLFB and UDS)	
XR-NTX will be superior to BUP-NX in producing abstinence from alcohol and other drugs
 
Significance/Rationale: Clinical trials show XR-NTX is effective for treatment of alcohol dependence, and naltrexone has some evidence of efficacy for stimulant dependence.

Cigarette smoking (FTND, Tobacco Use Questionnaire, VAS nicotine craving)	
XR-NTX will reduce cigarette smoking compared to BUP-NX
 
Significance/Rationale: Naltrexone has been studied as a treatment for nicotine dependence, with some support from clinical trials, although inconsistent. Given high morbidity and mortality associated with nicotine dependence, a comparative advantage of one or the other of these treatments at reducing smoking would be valuable to examine.

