12.10 Safety Analysis

Adverse events (AEs), including serious adverse events (SAEs), will be summarized by body system and preferred term using MedDRA (The Medical Dictionary for Regulatory Activities). Adverse events will be presented in two ways: (1) the number and proportion of participants experiencing at least one incidence of each event will be presented overall and by treatment group; and (2) a table displaying the total number of each event will be given overall and by treatment group. Listings of serious adverse events will be given, sorted by treatment, body system, and preferred term. Detail in these listings will include severity, relationship to study drug, and action taken as available. Treatment arm differences will be monitored by the DSMB.

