5.3.3 Primary Outcome Analysis Methods

Since the results of the interim analysis indicated a differential treatment initiation rate assessment, the data analysis modification will be employed. As noted in Section 3.2, if there is a differential treatment initiation rate in the early randomizers group, an interaction term for the treatment by randomization timing variables will be incorporated into the final analysis model.

Data will be analyzed using a Cox proportional hazards model. The model is as follows:

$$\log h(t | CUF) = \log h_0(t | CUF) + \beta_1 * Treatment + \beta_2 * TIMING + \beta_3 * CTP + \beta_4 * STRATA + \beta_5 * Treatment * TIMING$$

where h is the hazard rate, roughly defined as the probability per time unit that a case that has not relapsed to the beginning of the respective interval will relapse in that interval. Conceptually, it can be thought of as the number of relapse per time units in the respective interval, divided by the average number of non-relapse cases at the mid-point of the interval. The quantity h0 is an arbitrary baseline hazard rate.

The SAS PHREG procedure will perform survival analysis based on the Cox model to estimate the hazard ratio for the treatments. The 95% Wald Confidence limits will be estimated.

The following SAS Code will be used to analyze the data:

```
PROC PHREG;
    CLASS TREATMENT (REF='BUP-NX') TIMING (REF='Late');
    MODEL TIME*STATUS = TREATMENT TIMING CTP STRATA
    TREATMENT*TIMING;
    HAZARDRATIO TREATMENT;
RUN;
```

The variables included in the SAS code are described as follows:

- TREATMENT- This variable defines the randomized treatment assignment. (BUP-NX or XR-NTX)
- TIME- Time to relapse
- STATUS- Censoring variable
- CTP- CTP
- STRATA- Randomization Stratification factor pertaining to the baseline opioid severity level classified as <6 bags (Low Severity) or ≥ 6 bags (High Severity).
- TIMING- Binary baseline variable (early vs. later randomization as noted in Section 5.1 defined as either 'Late' or 'Early').

The initial analysis will be the construction of the asymptotic 95% CI for the hazard ratio of the difference between the treatment arms in the time to event distribution for the primary outcome. The study arm success rates with confidence intervals at week 24 and the difference in success rate at that time point and associated confidence intervals will be constructed.

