Adverse events (AEs), including serious adverse events (SAEs), will be summarized by body system and preferred term using MedDRA (The Medical Dictionary for Regulatory Activities) version 19.0 or higher. Adverse events will be presented in two ways: (1) the number and proportion of participants experiencing at least one incidence of each event will be presented overall and by treatment group. The incidence of adverse events and serious adverse events by

type will be compared between treatment arms using either Fisher's Exact mid-p-value or Chi-Square analysis as appropriate; and (2) a table displaying the total number of each event will be given overall and by treatment group. Listings of serious adverse events will be given, sorted by treatment, body system and preferred term. Detail in these listings will include severity, relationship to study drug, and action taken as available.

Treatment emergent AEs are defined as AEs occurring after participants have been inducted on study medication. Induction is defined as having had an injection if in the XR-NTX arm or having been dispensed medication if in the BUP-NX arm.

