Related			

*Note: Treatment emergence is defined as any adverse event that occurred after the study day of induction for those participants inducted onto study medication.

Table 34: Summary of Treatment Emergent* Serious Adverse Events by Treatment Arm			
	BUP-NX (N=)	XR-NTX (N=)	Total (N=)
Number of Participants Inducted			
Number of Participants with a Treatment Emergent Serious Adverse Event			
Number of Treatment Emergent Serious Adverse Events			
Type of Treatment Emergent Serious Adverse Event			
Death			
Life-threatening event			
Inpatient admission to hospital or prolongation of existing hospitalization			
Persistent or significant incapacity			
Congenital anomaly or birth defect			
Important medical event that required intervention to prevent any of the above			
Severity of Treatment Emergent Serious Adverse Event			
Grade 1-Mild			
Grade 2-Moderate			
Grade 3-Severe			
Relationship of Treatment Emergent Serious Adverse Event			
Not Related			
Related			

*Note: Treatment emergence is defined as any adverse events that occurred after the study day of induction for those participants inducted onto study medication.

Table 35: Summary of Treatment Emergent* MedDRA Coded Adverse Events by Treatment Arm			
System Organ Class/ Preferred Term (MedDRA v19.0 or higher)	BUP-NX (N=)	XR-NTX (N=)	Total (N=)
Participants with at least one treatment emergent adverse event			
Gastrointestinal disorders			
Constipation			
Vomiting			
Diarrhoea			
Nausea			
Toothache			
Abdominal pain upper			
Abdominal pain			
Glossitis			
Oral mucosal erythema			
Abdominal discomfort			
Glossodynia			
Gingival swelling			
Dyspepsia			
Abdominal pain lower			
Oral discomfort			
Mouth ulceration			
Lip swelling			
Psychiatric disorders			
Suicidal ideation			
Insomnia			
Anxiety			
Depression			
Depressed mood			
Suicide attempt			
Self injurious behavior			
Panic attack			
Depression suicidal			
Delirium			
Anhedonia			
Alcohol withdrawal syndrome			
Agitation			
Restlessness			
Psychotic disorder			
Paranoia			

Table 35: Summary of Treatment Emergent* MedDRA Coded Adverse Events by Treatment Arm			
System Organ Class/ Preferred Term (MedDRA v19.0 or higher)	BUP-NX (N=)	XR-NTX (N=)	Total (N=)
Mania			
Loss of libido			
Hypomania			
Affective disorder			
Drug abuse			
Nervous system disorders			
Headache			
Somnolence			
Syncope			
Migraine			
Dizziness			
Seizure			
Carpal tunnel syndrome			
Tremor			
Restless legs syndrome			
Paraesthesia			
Lethargy			
Hypoaesthesia			

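### The only AE/SAE and overdose summary shells (SAP Tables 33-36) count post-induction events in inducted participants, which is narrower than the by-arm comparison in the plan's text

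*SAP*

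**What the plan says.** **Text of the plan.** Protocol 5.2, objective 1b, lists among the domains to be compared between arms: "Safety, as measured by adverse events and serious adverse events, including opioid overdose episodes, both during the 6-month trial", and then the three-month follow-up. Protocol 12.10 plans the number and proportion of participants "experiencing at least one incidence of each event will be presented overall and by treatment group". SAP 7.4.1 repeats this and adds that the incidence of AEs and SAEs by "type will be compared between treatment arms", using Fisher's exact mid-p or chi-square. None of the three sets an induction condition. SAP 7.4.1 then gives a definition: "Treatment emergent AEs are defined as AEs occurring after participants have been inducted on study medication". It does not say that the summaries or tests are confined to such events.

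**Shells.** SAP Appendix A has four AE/SAE summary tables, 33 to 36, all titled as treatment emergent. The footnote to Table 33 reads: "Treatment emergence is defined as any adverse event that occurred after the study day of induction for those participants inducted onto study medication". Tables 34-36 carry it in nearly the same words. Overdose has a row in Tables 35 and 36 and in no other shell.

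**Induction.** The rationale for the induction outcome in Protocol 9.2 says: "Thus XR-NTX may have more dropouts after randomization but prior to XR-NTX induction". SAP 5.3.3 reports: "Since the results of the interim analysis indicated a differential treatment initiation rate assessment, the data analysis modification will be employed".

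**The concern.** Whether and when a participant is inducted is decided after randomisation, and the plan expects it to differ by arm. A count of events restricted to inducted participants, after induction, therefore leaves out a different share of each arm's experience. The reasons for induction failure in SAP Table 6 (leaving before induction, failing the naloxone challenge, meeting relapse criteria and others) show that those left out are not a random subset.

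Protocol 9.2 treats overdose documentation as essential safety data. If the safety report is built from the shells as printed, the by-arm overdose, SAE and AE figures will not answer objective 1b.

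There is also a conflict inside the SAP. The footnotes start the clock after the calendar day of induction, whereas 7.4.1 starts it once the participant has been inducted. A serious reaction a few hours after the first dose counts under 7.4.1 and is absent from Tables 33-36. Precipitated withdrawal is an example: the labelling in Protocol Appendix C (5.3) describes it as potentially needing hospitalisation, and Protocol 11.2.7 makes it reportable as an SAE when serious.

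**Working it through.** **1. Scope, side by side**

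| Place | Who and when | Output |
|---|---|---|
| Protocol 5.2, objective 1b | Both arms, trial and follow-up | Comparison, overdose included |
| Protocol 12.10 | No induction condition | Number and proportion by arm |
| SAP 7.4.1 | No induction condition | The same, plus tests |
| SAP Tables 33-36 | Inducted only, after induction day, no end date | By-arm summaries; overdose rows in 35 and 36 |
| SAP Table 38 | Non-treatment-emergent AEs in randomised participants | Listing by arm |
| SAP Tables 40, 41 | SAEs and deaths, no treatment-emergent limit | Listings by arm |
| SAP Table 43, one row | Suicidality-coded AEs, no treatment-emergent limit | By-arm count |
| SAP Table 4, two rows | Termination for an AE/SAE; death; randomised base | By-arm counts |

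The last two lines are the only by-arm AE, SAE or death counts outside Tables 33-36 that reach beyond the post-induction period, and none counts overdoses. Table 47 summarises withdrawal scores around the induction dose but does not count AEs or SAEs.

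**2. The planning values.** The plan states no figure for this point. The induction rates below come from the decision rule in Protocol 12.3: BUP-NX .85, difference .25, hence XR-NTX .60. The rule's stated power of more than 80% reproduces with 50 per arm (assumed equal split of 100) and one-sided 2.5%:
- pooled rate .725; null SE = √(2 × .725 × .275 / 50) = .0893
- alternative SE = √((.85 × .15 + .60 × .40) / 50) = .0857
- power = Φ((.25 − 1.96 × .0893) / .0857) = Φ(.87) ≈ .81

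**3. Headcount of never-inducted participants.** Protocol 12.2 projects about 250 early and 350 late randomizers, so about 125 and 175 per arm, 300 in all. Number never inducted = 125 × (1 − early rate) + 175 × (1 − late rate).

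| Late induction, BUP-NX / XR-NTX (assumed) | BUP-NX out | XR-NTX out |
|---|---|---|
| 1.00 / 1.00 | 125 × .15 = 18.75 (6.3%) | 125 × .40 = 50 (16.7%) |
| .85 / .85 | 18.75 + 26.25 = 45 (15%) | 50 + 26.25 = 76.25 (25.4%) |
| .95 / .85 | 18.75 + 8.75 = 27.5 (9.2%) | 50 + 26.25 = 76.25 (25.4%) |

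When late induction is equal in the arms, the excess on XR-NTX is 125 × .25 = 31.25 (10.4% of 300) for any BUP-NX early rate from .85 to 1.00. At 1.00 v .75 it is 0 v 31.25.

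**4. Why bias cannot be derived.** Suppose, purely for illustration, that event risk is equal in the arms among inducted participants and m times that among the never-inducted. Take the first row above, with shares out f = .1667 (XR-NTX) and .0625 (BUP-NX), and ignore events before or on induction day. The all-randomised risk ratio XR-NTX/BUP-NX is (1 − .1667 + .1667m) / (1 − .0625 + .0625m):
- m = 0.5: .9167/.9688 = 0.95
- m = 1: 1.00
- m = 2: 1.1667/1.0625 = 1.10
- m = 3: 1.3333/1.125 = 1.19

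The shells would show 1.00 throughout if their N= is inducted, or .8333/.9375 = 0.89 if it is randomised. The documents give neither m nor the denominator. Table 34 prints both an N= header and a row for the number inducted, which leans towards a randomised N= but does not settle it.

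**The case against.** The strongest reply is that this is a mismatch between text and shells, and that the text governs. SAP 7.4.1 already commits to by-arm proportions and tests with no induction limit. The shells are descriptive and do not exhaust the plan: Tables 15-18 show no hazard ratio or p-value, although SAP 5.3.3 specifies a Cox analysis. Treatment-emergent tables are conventional and fit the outcome label in Protocol 9.2, "Adverse Events related to study medications". Every SAE and death is listed by arm.

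Much of this stands. No data are lost, Tables 33-36 are worth keeping, and the absence of tests from the shells proves little. But a listing is not a by-arm summary, and if the text governs, the summary it describes still has no shell. The induction-day conflict remains even if treatment-emergent tables are accepted as sufficient.

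Three stronger readings are tempting and unsupported:
- **That the shells favour XR-NTX, or hide its overdoses.** No event rate is given for never-inducted participants, so no direction follows.
- **That Tables 33-36 report rates in inducted subsets.** That presumes a denominator the shells do not state. What holds under either denominator is that events are missing.
- **That the met trigger fixes the final induction gap.** SAP 5.2 checks induction once the 100 early randomizers have had at least 21 days, while induction stays open to week 22 (SAP 1.2).

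**Conclusion.** The point holds. The by-arm AE, SAE and overdose summaries described in objective 1b, Protocol 12.10 and SAP 7.4.1 have no matching shell. The shells that exist omit events before induction, on induction day and in the never-inducted, to an extent expected to differ by arm. Their footnote also contradicts 7.4.1 on induction-day events.

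The bias in any event rate is not derivable. The only size available is the headcount of about 50 XR-NTX and 19 BUP-NX never-inducted early randomizers. It rests on planning values, equal allocation and full late induction; it is not an observed rate, and it ignores pre-induction and induction-day events in those later inducted. This should be fixed before the safety tables are produced.

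**What to change.** 1. **Add by-arm shells for all randomised participants by assigned arm**, covering any AE, any SAE, overdose and death from Day 0 through the end of AE collection, with the treatment and follow-up periods shown separately as objective 1b implies. First reconcile the end of collection: Protocol Appendix A runs to 30 days after the last study visit, Appendix B to 30 days after the last active treatment visit. A fixed week 36 cut-off could drop late events that the present open-ended footnote counts.
2. **Apply the tests named in SAP 7.4.1 to SAEs, overdose and death.** Keep all-randomised AE counts descriptive, with a caveat: AEs are actively elicited at medical management visits (Protocol 11.2.7), which end at relapse (11.3.2), and SAP 3.2 expects induction failure to lead to relapse.
3. **Keep Tables 33-36 as supportive.** State whether N= is randomised or inducted, and align the footnotes with 7.4.1 so that post-dose events on induction day are counted. The listing shells show onset date only, so if onset time is not recorded, state a rule for same-day events.

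The cost is a few tables from data already captured and listed in Tables 38, 40 and 41, one footnote change, one denominator statement and one reconciliation of the collection window. The downside is that the added AE counts may be less complete in never-inducted participants.
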